#### **Analysis Populations**

Modified Intent-to-treat (mITT): all dyads that received at least one experimental session and completed at least one outcome assessment

MP-12 Statistical Analysis Plan Version 1: 26 February 2016

Per protocol (PP): all dyads that completed two experimental sessions and primary outcome assessment, and did not experience a major protocol deviation

Safety: all subjects who received any study treatment

# Handling of Dropouts, Missing Data

Dyads who discontinue treatment prior to completing the second experimental session and the primary endpoint will be replaced. These dropout subjects will be asked to complete an outcome assessment prior to continuing to the long-term follow-up.

Early termination visit data for mITT and Safety variables will be analyzed at the closest scheduled visit after the last experimental session completed. If the closest visit has valid data, the early termination data will be assigned to the next available visit. If a dyad discontinues and does not participate in an early termination visit, data from the last available visit will be used to replace the missing early termination visit data.

### Partial or Missing Dates:

The following conventions will be used to impute missing portions of dates for adverse events and concomitant medications. Note that the imputed values outlined here may not always provide the most conservative date. In those circumstances, the imputed value may be replaced by a date that will lead to a more conservative analysis.

#### Α. Start Dates

- 1) If the year is unknown, then the date will not be imputed and will be assigned a missing value.
- If the month is unknown, then: 2)
  - i) If the year matches the first dose date year, then impute the month and day of the first dose date.
  - ii) Otherwise, assign 'January.'
- 3) If the day is unknown, then:
  - i) If the month and year match the first dose date month and year, then impute the day of the first dose date.
  - ii) Otherwise, assign the first day of the month.

#### В. Stop Dates

- If the year is unknown, then the date will not be imputed and will be assigned a 1) missing value.
- If the month is unknown, then assign 'December.' 2)

3) If the day is unknown, then assign the last day of the month.

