5.2.3 Preparatory Psychotherapy Session (Visit 2 - Clinic Visit)

(Day 0)

CBCT Manual Sessions 1, 2 and 3

Sessions 1, 2 and 3 – Psychoeducation about PTSD, safety building for the relationship and beginning of communication skills.

This second Preparatory Session will last 90 minutes and take place at Visit 2. During the Preparatory Session:

- a. Therapists may record all sessions to audio and video. The PTSD+ participant and CSO participant will be given access to review audio or video recordings from the sessions upon request.
- b. Collect AEs and Medications, as described in Sections 8.0 and 9.0
- c. Confirm that the PTSD+ participant and CSO participant have appropriately tapered off of medications.
- d. Assess General Wellbeing
- e. Qualified study staff will administer the C-SSRS
- f. PCL-5 (last week) to assess PTSD symptoms for the PTSD+ participant and modified for the CSO participant to rate the PTSD+ participant.
- g. The PTSD+ participant, CSO participant, and therapists will discuss goals for the Experimental Session and will complete preparatory psychotherapy. Preparatory sessions will promote a safe setting for confronting trauma-related memories, emotions, and thoughts.
- h. Give the Reminder of Study Rules to the dyad, which includes instructions and restrictions for conduct prior to receiving the drug. The PTSD+ participant and CSO participant must agree to:
 - Ingest only alcohol-free liquids after 24:00 (midnight) the evening before the Experimental Session
 - Refrain from the use of any psychoactive drug, with the exception of caffeine or nicotine, within 24 hours of each Experimental Session
 - Not use caffeine or nicotine for two hours before and six hours after ingesting the drug, or until therapists deem it safe to do so

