#### **Protocol Deviations**

All protocol deviations will be included as a categorized listing. Safety and mITT analyses will include all enrolled dyads with all available data. Dyads with major deviations will be excluded from the per protocol analyses. Possible protocol deviations include the following seven categories:

- Subject entered study but did not meet criteria
- Subject developed withdrawal criteria but was not withdrawn
- Subject received excluded concomitant treatment
- Protocol procedure not performed per protocol
- Subject received incorrect treatment or incorrect dose
- Protocol procedure performed out of range
- Miscellaneous

The number of dyads in each protocol deviation category listed below will be summarized by MDMA group, and individual subjects will be listed in the appendix.

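### The SAP's partial-date rules can place an imputed start after a recorded stop, so an adverse event that ended before MDMA can be counted as treatment-emergent; imputed stops have no cap

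*SAP*

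**What the plan says.** SAP section 6.0, Partial or Missing Dates, gives one rule set for two kinds of record: "The following conventions will be used to impute missing portions of dates for adverse events and concomitant medications".

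Under A. Start Dates, rule 2(i) covers an unknown month: "If the year matches the first dose date year, then impute the month and day of the first dose date". Rule 3(i) covers an unknown day: "If the month and year match the first dose date month and year, then impute the day of the first dose date". Where there is no match, the start goes to January or to the first of the month. None of these rules mentions the stop date.

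Under B. Stop Dates, an unknown month becomes December. For an unknown day, "If the day is unknown, then assign the last day of the month". No upper limit is set.

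The preamble adds that, where the conventions do not give the most conservative date, "the imputed value may be replaced by a date that will lead to a more conservative analysis".

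SAP Safety Analyses makes adverse event reports the primary safety measure. It defines treatment-emergent events as those occurring after dosing, together with worsening of existing diagnoses.

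**The concern.** Moving an onset of unknown timing to the first-dose date is a sound convention: in doubt, the event is charged to the drug. It goes wrong when the record itself removes the doubt. If the stop date is known and precedes first dose, the onset must precede it too, whatever day is missing. Followed literally, rules A.2(i) and A.3(i) still put the start on the dosing day. The record then begins after it ended, and the event enters the treatment-emergent count.

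This trial has a pre-dose period in which such records can arise. Under Protocol 5.2.2, enrollment and the start of any medication taper come at Visit 1, and events that begin after enrollment are recorded as adverse events.

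The stop rules have a separate gap. Without a cap, an imputed stop can fall after the last time anyone saw the participant. Protocol 12.0 promises tables of duration for adverse events and concomitant medications. A start after the stop gives a negative duration, and an uncapped stop inflates it.

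**Working it through.** The plan states no figure on this point, so there is none to reproduce. The check applies the rules literally. The calendar dates are illustrative.

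**1. Start rules against a known stop.** Take first dose on 20 June 2017.

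- Start June 2017 (day unknown), stop known as 5 June. Rule A.3(i) gives a start of 20 June. Duration: 5 June − 20 June = −15 days.
- Start 2017 (month unknown), stop known as 20 April. Rule A.2(i) gives a start of 20 June. Duration: 20 April − 20 June = −61 days.

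If these are adverse events, the imputed onset is the dosing day and each would be counted as treatment-emergent. This assumes that a start on the dosing day counts as after dosing. The SAP gives no same-day rule, but imputing to that day has little purpose otherwise.

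**2. Do pre-dose events reach the database?** The documents differ.

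- Protocol 5.2.2 collects new events as adverse events from enrollment, and Table 3 ticks the row for all adverse events at Visits 1 and 2.
- Protocol 3.4 and 8.5 start collection of all adverse events on the day of drug administration. Both nevertheless collect psychiatric-status events throughout the study, and Table 3 ticks these from Visit 1.

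So at least psychiatric events between enrollment and dosing are captured on either reading.

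**3. How often rule A.3(i) fires.** Assume first-dose dates spread evenly over a 365-day year. An onset *b* days before dosing falls in the dosing month when the day of the month of dosing exceeds *b*. For *b* up to 28 the share is (365 − 12*b*)/365. Averaging over *b* = 1 to *L*, that is, onset uniform over the last *L* days:

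- *L* = 7: 1 − 12 × 4/365 = 87%
- *L* = 14: 1 − 12 × 7.5/365 = 75%
- *L* = 28: 1 − 12 × 14.5/365 = 52%
- *L* = 56: 26% (by direct count, since for *b* above 28 only the longer months contribute)

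These shares apply only to pre-dose events whose onset day is missing. Of those, only the ones with a recorded stop before first dose are provably misclassified. The rest are ambiguous, and imputing them to first dose is the conservative choice.

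**4. Stop rules against first dose.** With the same first dose of 20 June 2017:

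- Stop June 2017, day unknown: 30 June, after first dose.
- Stop May 2017, day unknown: 31 May, before first dose.
- Stop 2017, month unknown: 31 December 2017, after first dose.
- Stop 2016, month unknown: 31 December 2016, before first dose.

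An imputed stop therefore reaches first dose only when the stop month (day unknown) or stop year (month unknown) is that of dosing. Protocol 9.0 requires a gap of at least five half-lives plus one week. For a drug stopped exactly at the Table 7 washout plus 7 days, with the day unknown, the formula in step 3 gives the share of dosing dates on which the imputed stop is on or after first dose:

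- fluoxetine (45 + 7 = 52 days): 0%
- aripiprazole (23): (365 − 276)/365 = 24%
- citalopram (15): (365 − 180)/365 = 51%
- sertraline (13): (365 − 156)/365 = 57%
- alprazolam, lorazepam, venlafaxine (10): (365 − 120)/365 = 67%

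With the month unknown the share is (365 − gap)/365. It runs from 313/365 = 86% (fluoxetine, 52 days) to 357/365 = 98% (prazosin, 8 days).

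**5. Stop rules against last contact.** Take first dose on 10 January 2017 and the intervals in Table 3. Visit 10 is about 3 weeks later (31 January), Visit 15 about 4 weeks after that (28 February), and Visit 18 six months after Visit 15 (28 August). An event whose stop is recorded only as 2017 becomes 31 December 2017, which is 125 days after the last planned contact. A stop that was already recorded by then cannot lie there.

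**6. Does the override repair this?** It is optional, it does not define conservative, and it requires no check that start precedes stop. If conservative means more treatment-emergent events, it would leave the false one in place.

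**The case against.** The strongest reply is that imputing toward first dose errs on the safe side, in a trial with one treatment arm, descriptive adverse event tables and a full listing of events. A reader of the listing would see a stop before the start, and a careful programmer would query it. That limits the harm, but it does not defend a rule that contradicts a recorded date.

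Four stronger readings are tempting, and the documents do not support them.

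- A reader might infer that the stop rule also creates treatment-emergent events. It does not. The SAP's definition turns on occurrence after dosing, hence on onset; only the start rules can have this effect.
- A reader might infer that washed-out drugs become concomitant. SAP Prior and Concomitant Medications divides medications at informed consent, not at first dose. Tapering follows consent, so a tapered drug is already on the post-consent side whatever date is imputed.
- A reader might infer that dyads would be lost from the per-protocol set through the deviation category "Subject received excluded concomitant treatment". Nothing says that imputed dates decide deviations. Washout is checked prospectively, with medications reviewed before each session and confirmed by the study physician.
- A reader might want to cap drug stops at Visit 2, where the protocol says "Confirm that the PTSD+ participant and CSO participant have appropriately tapered off of medications". Table 3 makes Visit 2 Day 0 and first dose Day 1. A stop set to Visit 2 would sit one day before dosing and look like a breach of the Protocol 9.0 interval.

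**Conclusion.** Wrong as written; minor. Start rules A.2(i) and A.3(i) can produce a start later than a recorded stop, and for adverse events this can put an event that ended before MDMA into the treatment-emergent count. Imputed stops have no cap. They can pass last contact and, only when the stop month or year is that of dosing, first dose.

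The documents do not say how many partial dates to expect, so the number of affected records cannot be given. The shares above are conditional on a date being partial and rest on even dosing dates, together with uniform onset (for events) or a stop exactly at the minimum gap (for drugs). The conclusion does not depend on them: it follows from the wording of the rules and the definition of treatment-emergent.

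**What to change.** Add two rules to the SAP under Partial or Missing Dates.

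1. If a stop date is known and is earlier than the imputed start, the start is set no later than the stop. An adverse event known to have ended before first dose is not treatment-emergent. A stop with a missing day but a known month before the month of dosing should count as known for this purpose, since month-end is its latest possible date.
2. An imputed stop date is capped at the participant's last contact.

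Keep imputation to the first-dose date for onsets whose timing is truly unknown.

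The cost is a few sentences and a few lines of SAS. SAP 1.0 says the plan is finalized before any analysis, so the change belongs in the text before then.

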#### **Protocol Deviations**

All protocol deviations will be included as a categorized listing. Safety and mITT analyses will include all enrolled dyads with all available data. Dyads with major deviations will be excluded from the per protocol analyses. Possible protocol deviations include the following seven categories:

- Subject entered study but did not meet criteria
- Subject developed withdrawal criteria but was not withdrawn
- Subject received excluded concomitant treatment
- Protocol procedure not performed per protocol
- Subject received incorrect treatment or incorrect dose
- Protocol procedure performed out of range
- Miscellaneous

The number of dyads in each protocol deviation category listed below will be summarized by MDMA group, and individual subjects will be listed in the appendix.

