12.1 Statistical Power

This pilot RCT is the first study of its kind intended to establish preliminary effect size estimates of CBCT combined with MDMA-assisted psychotherapy for PTSD. In the absence of published effect sizes for this new treatment modality, effect sizes were estimated based on prior trials of these individual treatments. In a limited number of small pilot studies, CBCT for PTSD yielded paired-treatment effect sizes of g > 1.0 for improvements in PTSD on the primary outcome measure and co-morbid symptoms. The two completed controlled RCTs of MDMA-assisted psychotherapy for PTSD have yielded effect sizes of g > 1.0 for improvements in PTSD symptoms as well. Assuming that effect size of the combined treatment may be approximately 0.8, estimated power for a within-subject analysis with a significance level of .05 based on a 2-tailed test, is 62% for a sample size of 10 participants for the primary measure, suggesting the potential for an underpowered design, but with some possibility of detecting a within-subject effect due to treatment. Statistical power estimates were not available for secondary and exploratory measures, as they were previously not used in sponsor-supported studies.

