## 1. Primary Efficacy Analyses

The primary efficacy evaluation is a paired t-test of CAPS-5 Total Severity scores at baseline and the primary endpoint (visit 16) at an alpha level of 0.05. If the parametric assumptions for t-test analyses are not met, the analogous nonparametric methods will be used (Wilcoxon Rank-Sum).

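### The SAP restricts mITT and Safety to treated participants in one section and admits all enrolled dyads in another; followed literally, the second dilutes adverse-event incidence

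*SAP*

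**What the plan says.** Three statements define who is analyzed.

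- SAP, Analysis Populations: mITT is "all dyads that received at least one experimental session and completed at least one outcome assessment". Safety is everyone who received any study treatment. A per-protocol set is also defined.
- SAP, Protocol Deviations: "Safety and mITT analyses will include all enrolled dyads with all available data".
- Protocol 12.0 Data Analysis: the intent-to-treat analysis takes participants with one or more Experimental Sessions and follow-up assessments.

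Enrollment does not require dosing. The SAP's Subject Disposition and Dosing Summary treats a subject as enrolled once consent is signed and the eligibility criteria are completed. Protocol 5.2.2 enrolls the dyad at Visit 1. Tapering is started from there, Visit 2 follows, and the first dose is at Visit 3.

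For efficacy, the SAP specifies "a paired t-test of CAPS-5 Total Severity scores at baseline and the primary endpoint (visit 16) at an alpha level of 0.05" and names no population for it. For dropouts without an early termination visit, "data from the last available visit will be used to replace the missing early termination visit data". For safety, the SAP's Safety Analyses section counts events after dosing, plus medical-history conditions that worsen during the study.

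**The concern.** The two SAP statements produce different datasets whenever a dyad is enrolled and not dosed. The design makes this foreseeable, because participants on psychiatric medication have to taper between enrollment and the first session, and Protocol 4.1 allows extra time for that.

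Two programmers could follow the same SAP and obtain different safety denominators. The Safety and mITT sets also appear in the disposition and MDMA dosing summaries, where undosed people would change the figures again.

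For efficacy, a per-protocol and an mITT set both exist and the primary test is tied to neither, so the choice could be made after the data are seen. With about ten PTSD+ participants, one dyad is a tenth of the sample. The study's stated purpose is to obtain preliminary effect sizes and safety data, so the denominators matter more here than the p-value does.

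**Working it through.** **1. The plan's own figure.** Inputs from Protocol 12.1: "Assuming that effect size of the combined treatment may be approximately 0.8"; "a significance level of .05 based on a 2-tailed test"; power "is 62% for a sample size of 10 participants for the primary measure". For an exact paired t-test with 9 degrees of freedom, the noncentrality is 0.8 × √10 = 2.53, and power is 61.6%. This reproduces the stated 62%.

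**2. Assumption.** The documents give no number of enrolled but undosed dyads. I take k = 1 or 2, in two cases:

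- (a) the undosed dyads are among the 10 enrolled, as under Protocol 5.4, which does not replace dyads that discontinue treatment;
- (b) they are added to 10 dosed dyads, as under the SAP's Handling of Dropouts section, which does replace them.

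These replacement rules conflict, so the documents do not settle which case applies.

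**3. Adverse-event incidence if all enrolled dyads are in the denominator.** Let p be the true incidence among dosed people, with undosed people contributing no events. There are two people per dyad.

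- Case (a): shown incidence = p × (20 − 2k)/20
- Case (b): shown incidence = p × 20/(20 + 2k)

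With p = 50%:

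| k | Case (a) | Case (b) |
|---|---|---|
| 1 | 0.50 × 18/20 = 45% | 0.50 × 20/22 = 45.5% |
| 2 | 0.50 × 16/20 = 40% | 0.50 × 20/24 = 41.7% |

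The relative understatement is 10% and 20% in case (a), and 1 − 20/22 = 9.1% and 1 − 20/24 = 16.7% in case (b). It does not depend on p. A worsened medical-history condition in an undosed person could count as an event and would offset this slightly.

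**4. Primary estimate, conditional.** Suppose in addition that undosed dyads enter the paired test with the baseline CAPS-5 repeated at Visit 16, so that their change is exactly zero. The mean change, in SD units of change among dosed participants, is:

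| k | Case (a) | Case (b) |
|---|---|---|
| 1 | 0.80 × 9/10 = 0.72 | 0.80 × 10/11 = 0.73 |
| 2 | 0.80 × 8/10 = 0.64 | 0.80 × 10/12 = 0.67 |

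Power with the zeros included was simulated (400,000 runs; dosed changes normal with mean 0.8 and SD 1). The dosed-only comparison is the exact calculation of step 1.

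| k | (a) with zeros | (a) dosed only | (b) with zeros | (b) dosed only |
|---|---|---|---|---|
| 1 | 55.3% | 55.9% | 61.3% | 61.6% |
| 2 | 48.3% | 49.6% | 60.9% | 61.6% |

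The zeros cost 0.6 and 1.3 points in case (a), and 0.3 and 0.7 points in case (b). Simulated type I error in case (b) is 4.9% and 4.8%. Zero values pull down the mean but also the standard error, so the estimate moves much more than the test does.

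**The case against.** The best defense is that the sentence sits under Protocol Deviations and is followed at once by the rule that major deviations remove a dyad from the per-protocol set. In that place it may mean only that deviations remove nobody from Safety or mITT, with both labels keeping their earlier definitions. Protocol 12.0 also requires an Experimental Session. This is probably the intent, but the sentence does not say so, and its literal wording reaches undosed dyads. The objection therefore limits the fix to a wording change; it does not remove the contradiction.

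A reader might go further and infer that undosed dyads enter the primary test as zero change. The documents do not support that as a stated consequence. It would need every one of these to hold:

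- the Protocol Deviations sentence overrides the mITT definition;
- the unnamed primary population is mITT;
- carry-forward applies to a dyad with no completed experimental session, although the SAP places early termination data by reference to the last completed session;
- a screening CAPS-5 is carried to Visit 16, although the SAP's rule draws on the last available visit, which for an undosed dyad is Visit 1 or 2, and Table 3 schedules no CAPS at either;
- no later CAPS is obtained, although the SAP asks dropouts for an outcome assessment and Protocol 5.4 seeks one where possible.

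The sentence also refers to available data. On the natural reading, an undosed dyad without a Visit 16 CAPS-5 gives no pair and drops out of the paired test.

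**Conclusion.** The contradiction between the two SAP sections is real, and the Protocol Deviations sentence also disagrees with Protocol 12.0.

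The firm consequence is for safety. If that sentence is followed as written, adverse-event incidence is understated by 10% or 20% in relative terms with 1 or 2 of 10 enrolled dyads undosed, and by about 9% or 17% if those dyads come on top of 10 dosed ones. These sizes rest on an assumed count and on which replacement rule applies. If every enrolled dyad is dosed, there is no effect on incidence.

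The efficacy consequence is conditional. A fall from 0.80 SD to between 0.64 and 0.73 needs the whole chain listed above, which the SAP does not clearly provide for. Even then the significance test is nearly unchanged. What stands on the efficacy side without any such chain is that no population is named for the primary test. The point should be corrected before analysis, but it is no threat to the validity of the paired test.

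**What to change.** 1. SAP, Protocol Deviations: replace the sentence with *Protocol deviations do not exclude dyads from the mITT and Safety populations as defined under Analysis Populations.* Simply deleting the reference to enrolled dyads would break the sentence and lose the useful rule that deviations do not exclude anyone from these sets.
2. SAP, Subject Disposition and Dosing Summary: state that enrolled but undosed dyads are reported in disposition only.
3. SAP, Primary Efficacy Analyses: state that the paired test uses mITT as defined under Analysis Populations, with per protocol as a sensitivity analysis.

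In the same edit it would help to say whether study treatment in the Safety definition means MDMA. As worded, a dyad with only preparatory therapy could arguably qualify. The replacement rules in the SAP and Protocol 5.4 also need to be reconciled, since they decide which denominator applies.

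The cost is a few sentences in the SAP. Data collection, visits and sample size are unaffected.
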